4.3 Sample Size

A total of 220 eligible adult participants will be randomized. The sample size for the study is not based on any statistical hypothesis testing. The sample sizes for each group were selected and weighted toward the higher antigen and adjuvant dose combinations to ensure that the safety assessment in each group at the interim analysis was adequate to advance to an infant Phase 2 trial and would reflect the probability for similar dose ranges to be included in a study in infants. With 40, 60, and 80 adults vaccinated per group, the probabilities of observing at least one unsolicited AE, solicited local AE, or solicited systemic AE when the true event rates are 0.5%, 1%, and 5%, respectively, are presented in Table 4. For example, if the true AE rate is 5%, with 60 participants in a treatment group, there is a 95% probability of observing at least one AE.

Table 4: Probability of Observing at Least One Unsolicited AE, Solicited Local AE, or Solicited Systemic AE by Assumed True Event Rates

Sample Size Per Group	Assumed True Event Rate		
	0.5%	1.0%	5.0%
N = 40	0.182	0.331	0.871
N = 60	0.260	0.453	0.954
N = 80	0.330	0.552	0.983

The expected precision of GMC ratio between the IVT PCV-25 and Prevnam 20 groups at the first (interim) analysis is presented in Table 5 below.

Table 5: Expected Precision of GMC Ratio by Assumed Standard Deviation (SD) of Log₁₀ Antibody Concentration and GMC Ratio with Different Sample Sizes

Assumed SD of log ₁₀ Antibody Concentration in IVT PCV-25 group	Assumed SD of log ₁₀ Antibody Concentration in Prevnar 20	Assumed GMC Ratio (IVT PCV-25 vs. Prevnar 20)	Expected 95% CI for GMC Ratio		
			N ₁ :N ₂ = 20:20	N ₁ :N ₂ = 30:20	N ₁ :N ₂ = 40:20
0.3	0.20	0.5	0.34-0.75	0.35-0.71	0.36-0.69
		0.75	0.50-1.12	0.53-1.06	0.55-1.03
		1.0	0.67-1.49	0.71-1.41	0.73-1.37
	0.25	0.5	0.32-0.77	0.34-0.73	0.35-0.72
		0.75	0.49-1.15	0.51-1.10	0.52-1.07
		1.0	0.65-1.54	0.68-1.47	0.70-1.43
	0.30	0.5	0.31-0.80	0.33-0.77	0.33-0.75
		0.75	0.47-1.20	0.49-1.15	0.50-1.12
		1.0	0.63-1.60	0.65-1.53	0.67-1.50
0.4	0.30	0.5	0.29-0.87	0.31-0.81	0.32-0.78
		0.75	0.43-1.30	0.46-1.22	0.48-1.18
		1.0	0.58-1.74	0.62-1.63	0.64-1.57
	0.35g	0.5	0.28-0.90	0.30-0.85	0.31-0.82
		0.75	0.42-1.35	0.44-1.27	0.46-1.23
		1.0	0.56-1.80	0.59-1.69	0.61-1.64
	0.40	0.5	0.27-0.93	0.28-0.88	0.29-0.86
		0.75	0.40-1.40	0.42-1.32	0.44-1.29
		1.0	0.54-1.87	0.57-1.76	0.58-1.72
0.5	0.40	0.5	0.25-1.01	0.27-0.94	0.28-0.90
		0.75	0.37-1.52	0.40-1.40	0.42-1.35
		1.0	0.49-2.03	0.53-1.87	0.56-1.79
	0.45	0.5	0.24-1.05	0.26-0.97	0.27-0.94
		0.75	0.36-1.58	0.38-1.46	0.40-1.41
		1.0	0.48-2.10	0.51-1.95	0.53-1.88
	0.50	0.5	0.23-1.09	0.25-1.02	0.25-0.98
		0.75	0.34-1.64	0.37-1.53	0.38-1.47
		1.0	0.46-2.18	0.49-2.03	0.51-1.96
0.6	0.50	0.5	0.21-1.18	0.23-1.08	0.24-1.03
		0.75	0.32-1.78	0.35-1.62	0.37-1.54
		1.0	0.42-2.37	0.46-2.15	0.49-2.05
	0.55	0.5	0.20-1.23	0.22-1.12	0.23-1.07
		0.75	0.31-1.84	0.33-1.68	0.35-1.61
		1.0	0.41-2.45	0.45-2.25	0.47-2.15
	0.60	0.5	0.20-1.27	0.21-1.17	0.22-1.12
		0.75	0.29-1.91	0.32-1.76	0.33-1.69
		1.0	0.39-2.55	0.43-2.34	0.44-2.25

Note: CI = confidence interval; N₁ is the sample size in the IVT PCV-25 group; N₂ is the sample size in the Prevnar

20 group. An attrition rate of 10% was used in calculating the expected 95% CIs.

If the true SD of \log_{10} antibody concentrations for a specific serotype is 0.5 in the IVT PCV-25 group and 0.45 in the Prevnar 20 group and the true GMC ratio between the two groups is 0.75, the expected two-sided 95% CI for the GMC ratio between the two groups is (0.36, 1.58) with 18 evaluable participants per group, (0.38, 1.46) with 27 evaluable participants in the IVT PCV-25 group and 18 evaluable participants in the Prevnar group, and (0.40, 1.41) with 36 evaluable participants in the IVT PCV-25 group and 18 evaluable participants in the Prevnar group.

4.4 Study Cohorts

4.4.1 Enrolled Population

All subjects who provide written informed consent, regardless of the subject's screening, randomization, and treatment status in the study.

4.4.2 Exposed Population

All subjects in the enrolled population who were randomized and received a vaccination dose (i.e., were accrued).

4.4.3 Safety Analysis Population

All subjects in the exposed population for whom any safety data is available. All safety analyses will be performed using this population. The denominators for different safety endpoints may vary according to the number of subjects with available data for the specific endpoint. For instance, the solicited local and systemic adverse event endpoint will be based only on those who have the corresponding CRF data regardless of other safety data. Treatment groups for safety analysis will be assigned according to the actual treatment received.

4.4.4 Full Analysis Population

This population will include all subjects in the exposed population for whom any post-study vaccine administration immunogenicity results are available. If it differs from the per protocol population, an immunogenicity analysis will also be performed using this population as a sensitivity analysis to support the robustness of the final results. The analysis based on this population will serve as supportive results for all secondary immunogenicity objectives. Subjects in the full analysis (FA) population will be analyzed as randomized, i.e., according to the treatment group to which subjects were assigned.

4.4.5 Per Protocol Population

This population will include all subjects in the FA population who were correctly vaccinated per randomization and have no protocol deviations that are determined to potentially interfere with the immunogenicity assessment of study vaccine.

The per protocol (PP) population will serve as the primary analysis population for the (secondary) immunogenicity endpoints. The population will be adapted by time point to include subjects' data up to

the time of disqualifying protocol deviation or discontinuation. The criteria for exclusion of subjects from the PP population will include the following:

- Missed vaccinations
- Significant non-compliance with visit windows
- Any eligibility criteria not met
- Receipt of a non-study vaccine
- Receipt of immunosuppressants or immune modulators
- Receipt of study vaccine not stored as per manufacturers approved storage condition
- Incomplete vaccine dose administration
- Serological results unavailability
- Incorrect randomization
- Dosed with incorrect study product

This list is not exhaustive, as unexpected deviations may arise requiring unique consideration and will be reviewed by a blinded adjudication committee prior to the interim analysis.

4.5 Blinding

This is an observer-blind clinical trial where unblinded study personnel will be responsible for preparing study vaccine doses in accordance with the randomly determined assignment, administering the study vaccines, and handling all vaccine accountability procedures. Unblinded personnel will not participate in the other aspects of the clinical trial after vaccine administration, to help ensure the integrity of the blind at the site. The unblinded personnel will not reveal participants' randomization assignments to the participants, or staff associated with the Sponsor, PATH, CRO, or site.

Emergency unblinding decisions are expected to be rare and could be justified only when that information is needed for the future clinical management of that participant. The decision of emergency unblinding must be approved by the principal investigator (PI) and the sponsor after sufficient evaluation. If a subject's treatment assignment is unblinded, the subject will remain in the study and continue with protocol-defined study visits and procedures, unless there is another reason for subject discontinuation. The safety data collected after the unblinding will be reported separately. The decision to unblind will be communicated to all regulatory bodies as required. At the end of the study, documentation of all unblinded subjects (and the rationale for unblinding) will be incorporated into the trial master file (TMF).

For the first, interim analysis, an independent CRO statistician and programmer team (whose responsibilities are otherwise limited to supporting the DSMB) will be unblinded to conduct the analyses. Study unblinding will be conducted and documented in accordance with relevant CRO SOPs. The independent CRO statistician and programmer team will provide the unblinded group-level safety report directly to the Sponsor, its consultants, PATH, the Bill & Melinda Gates Foundation, and the site investigators. The independent CRO statistician and programmer team will provide the unblinded group-level and individual-level (participant ID masked) serotype-specific IgG responses to the Sponsor, its consultants, PATH, and the Bill & Melinda Gates Foundation. All other personnel will continue to remain blinded to individual treatment assignments until all subjects complete Visit 4 and the database is locked.

The second analysis will include both group-level and individual-level (with participant ID-masked) serotype-specific OPA results. Unblinded group-level second analysis will be shared with the Sponsor and its consultants, PATH, the Investigators, and representatives from the Bill & Melinda Gates Foundation. The individual-level, participant ID-masked results will be shared with the Sponsor and its consultants, PATH, and representatives from the Bill & Melinda Gates Foundation as they become available.

4.6 Estimands and Analytical Methodology

4.6.1 Estimands

The estimands corresponding to each primary and secondary objective are described in Table 1 and Table 2 in Section 2.3.

For the primary safety estimand, receipt of concomitant medications will be handled with treatment policy strategy, which means that participants who take concomitant medications will be included in the safety analysis. The estimates will be calculated based on the safety analysis population.

For the estimand to evaluate the immunogenicity objective, receipt of immune-modifying medications/vaccines/treatments will be handled according to principal stratum strategy, which means participants who receive immune-modifying medications/vaccines/treatments will not be included in the primary immunogenicity analysis. The corresponding estimates will be computed based on both PP and Full Analysis populations, to examine robustness of the estimates. Immunogenicity results that are below the lower limit of quantification (LLOQ) will be set to half of the LLOQ (LLOQ/2) in the analysis. Immunogenicity results above the upper limit of quantification (ULOQ) will be set to the ULOQ in the analysis.

4.6.2 Descriptive Methodology

When appropriate, continuous data will be summarized using descriptive statistics such as number of participants with non-missing values, mean, standard deviation (SD), median, minimum, and maximum. Categorical data will be presented using the percentage of participants in each category. A two-sided 95% CI will be provided for estimates, as appropriate. Individual participant data will be provided in listings.

4.6.3 Analysis Sequence

Upon completion of the Day 29 Visit 3 from all 220 participants, the CRO will prepare an unblinded safety report for review and approval by the DSMB to continue the study as planned.

There will be three analyses. The first analysis (interim) includes the dataset of the safety from all participants having completed the Day 29 visit, and the serotype-specific IgG responses from approximately 50% or more of the participants having completed the Day 29 visit, in order to provide the Sponsor an initial indication of the comparative immunogenicity among the three different IVT PCV-25 formulations and to compare to the immune responses elicited in participants vaccinated with Prevnar 20™.

The Sponsor and its consultants, PATH, and representatives from the Bill & Melinda Gates Foundation will review both group-level and individual-level (with participant ID masked) serotype-specific IgG antibody responses (baseline and Day 29) from the interim analysis, and the group-level unblinded safety data to ensure that both the safety profile and the immune responses to IVT PCV-25 are sufficient to proceed to planning for a Phase 2 study in infants. The Investigators will be provided the group-level safety and immunogenicity results. All site and CRO personnel will remain blinded to individual treatment assignment until end of study.

The second analysis will be conducted once serotype-specific OPA data from the baseline and Day 29 visits from all 220 participants become available and will include both group-level and individual-level (with participant ID-masked) serotype-specific OPA results. The unblinded group-level second analysis will be shared with the Sponsor and its consultants, PATH, the Investigators, and representatives from the Bill & Melinda Gates Foundation. The individual-level, participant ID-masked results will be shared with the Sponsor and its consultants, PATH, and representatives from the Bill & Melinda Gates Foundation as they become available.

The third and final analysis will include all late safety events from all participants through Day 169 (end of study) with the complete IgG and OPA immunogenicity results from all participants. This will occur after all safety data through Visit 4 from all 220 participants have been collected following the adult LSLV (Visit 4). The database will be cleaned and locked, and a final analysis of all data will be performed.

4.6.4 Analysis of Demographic and Baseline Characteristics

Demographics and baseline characteristics, including age, height, weight, sex, race, and ethnicity will be summarized for both the exposed and per protocol populations by treatment group.

For the exposed population, the number and percentage of participants with medical history will be tabulated by MedDRA System Organ Class (SOC), Preferred Term (PT) and treatment group. Using the WHO DD, the number and percentage of participants with concomitant medications will be tabulated by anatomical therapeutic chemical (ATC) classification, preferred drug name and treatment group.

Summaries of participant disposition will be prepared for all participants, including the number and percent enrolled, screened, randomized, and administered study vaccine, as well as a Consolidated Standards of Reporting Trials (CONSORT) diagram describing study participation and discontinuation. The reasons for screen failures and discontinuations will be summarized and listed.

A summary and listing of visit attendance will be prepared, in addition to a summary and listing of study vaccine administration and sample collection/availability for each sample.

4.6.5 Analysis of Primary Objective

All safety analyses will be conducted in the safety analysis population, according to the treatment received. Frequencies and percentages of participants with any solicited AE, solicited local AE, solicited systemic AE, unsolicited AE, clinical safety laboratory abnormality, SAE will be tabulated along with an exact two-sided 95% CI computed via the Clopper-Pearson method. The denominators for percentages

will be the number of participants with the data available for analysis for the given endpoint. Participant-level data listing will be provided.

Solicited local and systemic AEs: All solicited AEs reported during 7 days post vaccination will be summarized according to defined severity grading scales. Frequencies and percentages of participants experiencing each solicited AE will be presented by treatment group and severity.

Hematological and biochemical measurements: For clinical safety laboratory data collected at screening and 7 days post-vaccination, individual Hgb, WBC count, Plts, AST, ALT, and creatinine values will be graded according to Table 10 and summarized by toxicity grading and study group. In addition, summaries of changes from baseline will be presented. Clinically significant laboratory abnormalities will be considered an AE and relatedness will be reported.

Unsolicited AEs: All unsolicited AEs with onset occurring during the first 28 days post vaccination will be assessed for severity and relatedness to study product by the PI. Frequencies and percentages of participants with unsolicited AEs will be summarized by the SOC, PT, and treatment group. Similar summaries will be provided for severity and relatedness of the unsolicited AEs.

SAEs: All SAEs through Visit 4 (Day 169) will be recorded and summarized. Frequencies and percentages of participants with SAEs and relatedness to study vaccine of the events will be summarized by SOC, PT, and treatment group.

When an AE occurs more than once for a participant, the participant will be only counted once for the corresponding PT according to the maximum severity of the events. A summary table will be prepared for unsolicited AEs comprised of the following categories:

- Unsolicited AEs
- Related unsolicited AEs
- SAEs
- Related SAEs
- SAEs leading to death
- Unsolicited AEs leading to participant discontinuation

All reported AEs that start after vaccination will be tabulated. If a given disease/condition is already reported as ongoing at the first visit on the medical history form, it will be counted and tabulated as an AE only if it worsens after vaccination with the study vaccines.

Onset day, duration, and outcome of unsolicited AEs will be summarized by treatment group. For SAEs, seriousness criteria will be summarized as well.

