### **8.1 Collection of Safety Events**

AEs will be systematically collected at all study visits. Solicited AEs will be assessed in all participants immediately (30 minutes) after each vaccination. Subjects will record solicited AEs daily in the memory aid for the 7 days (Day 1 and the following 6 days) following vaccination, as well as record unsolicited AEs that occur prior to the 7- or 28-day follow-up visit (If a solicited AE is ongoing at 7 days post-vaccination, or occurs after 7 days post-vaccination, the event will be followed as per AE monitoring requirements. Clinically significant laboratory abnormalities in adult participants will also be recorded as an unsolicited AE.

SAEs will be recorded throughout the entire study period.

Medical events which occur between the time of enrollment (signed informed consent) and randomization for all participants regardless of screening outcome will be captured on the medical history form.

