### 8.2.3 Unsolicited AE

An unsolicited adverse event is any AE reported spontaneously by the participant, observed by the study staff during study visits, or those identified during review of medical records or source documents. Solicited AEs with an onset after the 7-day solicitation period will be considered unsolicited AEs. In the absence of a diagnosis, abnormal physical examination findings, or abnormal clinical safety laboratory test results that are assessed by the investigator to be clinically significant will be recorded as an AE.

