### 8.2.5 Severity (Intensity) of an AE

The severity of all solicited AEs will be graded from Mild (Grade 1) to Potentially Life Threatening (Grade 4), based on the criteria given in Appendix 2. All AEs leading to death are Grade 5 events. AEs are graded based on the worst severity grade during the illness/symptoms. All other unsolicited AEs will be classified as an AE and graded based on the AE severity scale in Table 11 below. The grading scales for solicited and unsolicited AEs used in this study have been derived from the *Division of AIDS (DAIDS) Table for Grading the Severity of Adult and Pediatric Adverse Events* (Version 2.1, July 2017), from the US National Institutes of Health, and from *Guidance for Industry, Toxicity Grading Scale for Healthy Adult and Adolescent Volunteers Enrolled in Preventive Vaccine Clinical Trials*, U.S. Department of Health and Human Services, FDA, CBER, September 2007.

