2.3 Study Endpoints and Estimands

2.3.1 Primary: Safety and Tolerability

Table 1: Primary Endpoints and Estimands

ENDPOINTS	ESTIMANDS
-----------	-----------

 1. Local reactions (redness, swelling, and pain at the injection site) 2. Systemic events (fever, headache, fatigue, muscle pain, joint pain, and rash) 3. Unsolicited Adverse events (AEs) 4. Serious adverse events (SAEs) 	
Population: Healthy pneumococcal vaccine-naïve adult participants receiving study vaccines
 
Population-level summary:
 
 1. Number and severity of solicited local reactions within 7 days after vaccination (redness, swelling, and pain at the injection site) by group 2. Number and severity of solicited systemic AEs within 7 days after vaccination by group 3. Number and severity of unsolicited AEs within 28 days after vaccination by group 4. Number of SAEs within 6 months after vaccination by group
---	---

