4.9 Conventions for Presentation

The conventions for presentation in the analysis displays are shown in Table 6.

Table 6: Conventions for Presentation

Convention	Description
Decimals for summary statistics	General rule: Relative to number of decimals in original data, use 1 more decimal for mean, median, and percentiles, 2 more decimals for standard deviation/error, and same number for minimum, maximum, and range. Do not exceed 4 decimals. Some laboratory parameters or other data may require judicious deviation from this rule
Format for percentages	Display percentages with 1 decimal. When the percentage is low, the number of decimals could be increased appropriately.

The conventions for calculation and tabulation are shown in Table 7.

Table 7: Conventions for Calculation and Tabulation

Convention	Description
Age Calculation	Age is calculated as the difference between the subject's date of informed consent and the date of birth with one decimal place. If only the year of birth is reported, age is calculated as the difference between year of informed consent and year of birth.
Duration Calculation	Duration of an event is calculated as end date – start date + 1. Duration of an ongoing event or event with unknown start date is considered missing.
Percentage calculation	Percentages are calculated as $100 \times \text{numerator} / \text{denominator}$. Rounding is not necessary because rounding is handled by the display format. Denominator is total number of subjects with non-missing data unless specified otherwise in a particular analysis display specification.

5 Appendices

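### SAP Table 7 drops events still ongoing at data cut from the unsolicited-AE duration summary, and the course of solicited reactions after Day 7 has neither a by-group display nor a settled grading rule

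*SAP*

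**What the plan says.** **Duration.** SAP 4.6.5 plans that "Onset day, duration, and outcome of unsolicited AEs will be summarized by treatment group". SAP 4.9 (Table 7) computes duration as end date minus start date plus one and adds: "Duration of an ongoing event or event with unknown start date is considered missing". No duration summary is planned for solicited AEs.

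**Solicited reactions.** The primary estimands in SAP 2.3.1 are "Number and severity of solicited local reactions within 7 days after vaccination" and "Number and severity of solicited systemic AEs within 7 days after vaccination by group". SAP 4.6.5 follows them: "All solicited AEs reported during 7 days post vaccination will be summarized according to defined severity grading scales".

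**After Day 7.** For a solicited reaction still present at 7 days, Protocol 8.1 says "the event will be followed as per AE monitoring requirements". Protocol 8.2.3 reclassifies late starters only: "Solicited AEs with an onset after the 7-day solicitation period will be considered unsolicited AEs". On severity, Protocol 8.2.5 says that "AEs are graded based on the worst severity grade during the illness/symptoms", with no limit to the first week.

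**The concern.** Two separate matters arise.

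The first is a rule that loses information selectively. An event is ongoing because it has not yet ended, so setting its duration to missing removes cases according to their length. What remains in the by-group summary is weighted towards events that ended quickly. This matters most at the first analysis, which covers safety through Day 29, functions as the primary analysis (Protocol 1.8) and informs planning for infants (SAP 4.6.3).

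The second is a gap. The protocol expects some solicited reactions to outlast the diary: participants are told to call if reactogenicity is ongoing on Day 8 (Protocol 6.2.2), and such events are followed. The trial compares antigen and adjuvant doses, and persistence or late worsening is one way in which formulations could differ. The documents do not say which by-group table shows that later course, or whether a later peak changes the tabulated grade. Duration is evidently regarded as relevant to safety, because pause Rule 3 depends on how long fever or injection-site pain lasts.

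**Working it through.** **1. Where each kind of event goes.** The days are illustrative; the solicitation period is Days 1–7.

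| Event | Table under the plan | Duration |
|---|---|---|
| Solicited, onset Day 3, ends Day 12 | 7-day solicited table; later course has no by-group display | Computable (12 − 3 + 1 = 10 days), but no solicited summary planned |
| Solicited type, onset Day 9 | Unsolicited tables (Protocol 8.2.3) | In the unsolicited summary once ended |
| Unsolicited, onset Day 20, ongoing at the Day 29 cut | Unsolicited tables | Missing at the interim |
| The same event, end date recorded as Day 40 | Unsolicited tables | 40 − 20 + 1 = 21 days at the final analysis |

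So Table 7 affects the unsolicited summary, and only for events without an end at the cut.

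**2. Direction and possible size of the duration effect.** The documents give no AE durations, so these five are invented. Four events last 1, 2, 3 and 4 days. One starts on Day 5 and is ongoing at Day 29, so it has lasted at least 29 − 5 + 1 = 25 days.

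- Table 7 rule: n = 4, mean (1+2+3+4)/4 = 2.5, median 2.5, maximum 4.
- Ongoing event kept at its minimum: n = 5, mean at least (1+2+3+4+25)/5 = 7.0, median 3, maximum at least 25.
- Kaplan-Meier with that event censored at 25 days: survival is 0.8, 0.6 and 0.4 after Days 1, 2 and 3, so the median is 3 days.

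The mean and maximum move far, the median little. SAP 4.6.2 lists all three for continuous data, as appropriate, without fixing one for duration.

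**3. The two severity rules side by side.** Take a swelling that starts on Day 6, is Grade 1 on Day 7 and Grade 3 on Day 9. If the 7-day limit in SAP 2.3.1 and 4.6.5 applies to the grade, it is tabulated as Grade 1. If that limit only selects which events count, and Protocol 8.2.5 sets the grade, it is tabulated as Grade 3. Neither document chooses.

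**4. How many participants could be involved.** The nearest figure in the plan is SAP Table 4, the chance of at least one event, 1 − (1 − p)^N. For N = 60 and p = 5% this gives 0.9539 against the printed 0.954; all nine cells reproduce. No printed figure changes under this point.

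The documents give no rate for a worst grade first reached after Day 7. The same formula with an assumed share q gives:

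| q (assumed) | N = 40: expected; P(at least one) | N = 60 | N = 80 |
|---|---|---|---|
| 1% | 0.4; 0.33 | 0.6; 0.45 | 0.8; 0.55 |
| 2% | 0.8; 0.55 | 1.2; 0.70 | 1.6; 0.80 |
| 5% | 2.0; 0.87 | 3.0; 0.95 | 4.0; 0.98 |

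For persistence, Protocol Table 6 reports a local reaction in 54 of 60 Phase 1 participants (90%). Applied here, 0.90 × 220 = 198. If 2% to 10% of these were ongoing after Day 7 (assumption), about 4 to 20 participants would be concerned. One participant is 2.5 percentage points in a group of 40.

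**The case against.** A reader might infer that reactions lasting beyond Day 7 enter no table, and that the primary endpoint therefore understates severity and duration. The documents do not support this, for four reasons.

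- A reaction starting on Days 1–7 is in the solicited table, and one starting later is in the unsolicited tables. SAP 4.6.5 also commits to tabulating every AE that starts after vaccination and to participant-level listings.
- The primary estimand is number and severity within 7 days. Duration is not in it, and Table 7 bears only on the unsolicited summary.
- Understated severity would require the grade to be frozen at Day 7. The SAP does not say that, and Protocol 8.2.5 may carry a later peak into the table.
- Table 7 does not reach every reaction present on Day 8, only events without an end at the cut.

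All four stand.

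The duration loss is also visible and partly temporary. Outcome is summarised beside duration and has an ongoing category (Protocol 8.2.7), and ongoing unsolicited AEs are reviewed at Visit 4 (Protocol 6.2.5). That stands too, but a count of ongoing events in another column does not correct the duration figure, and the later review does not help the interim.

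Other routes watch for late worsening: injection-site assessment at Visit 2, weekly notices of Grade 3 or greater AEs, and the pause rules. These protect participants but do not give a comparison by group.

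Finally, the numbers are weak. The Phase 1 rate pools both arms, used an earlier formulation and is almost all pain; swelling occurred in 2 of 60, with no Grade 3 local reaction. The assumed rates have no source. This is right, and they should be read only as a scale.

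**Conclusion.** The Table 7 point holds as a matter of the stated rule. Followed as written, it removes unresolved events from the by-group unsolicited duration summary and shortens it, chiefly at the Day 29 interim. The direction rests on unresolved events being typically the longer ones; the amount cannot be derived from the documents.

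The second point holds as an omission and an unreconciled pair of rules: no by-group display is specified for the post-Day-7 course of reactions that began in the window, and the 7-day severity limit is not squared with worst-grade grading. It is not a demonstrated bias in the primary endpoint.

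The trial is descriptive, and no sample size, power or error rate is affected. Minor severity; a cheap improvement.

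**What to change.** **SAP Table 7.** Treat an ongoing event as right-censored at last contact or data cut. Report the number ongoing beside each duration summary, for example with a Kaplan-Meier median; a simpler display would do if it shows the ongoing count and does not discard those events. Keep the missing rule for unknown start dates only.

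**SAP 4.6.5.** Keep the 7-day table as the estimand. State whether a grade reached after Day 7 by a reaction that began on Days 1–7 counts in that table, so that the section agrees with Protocol 8.2.5. Add by group, for solicited AEs with onset on Days 1–7, the number and percentage still ongoing after Day 7 and, as far as the follow-up data record it, the worst grade through resolution or last contact.

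**Cost.** A few sentences and one or two extra tables. Protocol 8.1 already requires the follow-up, but the diary solicits reactions for 7 days only and the documents do not show whether the CRF holds a later peak grade, so check that first. Reported durations may look slightly less favourable.
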